4.2 Exclusion Criteria

- Severe heart failure (NYHA class \geq III);
- Uncontrolled hypertension ($\geq 180/110$ mmHg);
- First-degree atrioventricular block on awake ECG (PR interval ≥ 0.20 s), or occurrence of Mobitz type II second-degree or third-degree AV block at any time;
- 24-hour average heart rate ≤ 50 beats per minute, RR interval ≥ 3 s, or history of syncope unrelated to the current ACS;
- Patients on dialysis;
- History of renal denervation or vagal ganglion ablation therapy;
- Life expectancy less than 4 months;
- Pre-existing clinical diagnosis of other severe psychiatric disorders prior to PCI, including schizophrenia, severe intellectual disability, substance abuse;
- Patient currently taking antipsychotic medications;
- High suicide risk;
- Pregnant or lactating women;
- Left ear disease, acute exacerbation of asthma or chronic obstructive pulmonary disease, or other conditions precluding taVNS treatment;
- Presence of cardiac pacemaker, implantable cardioverter-defibrillator (ICD), or other implantable stimulators (e.g., VNS or deep brain stimulators).

4.3 Withdrawal Criteria

Desire to pursue other treatments or voluntary withdrawal from the trial without specific reason.

5. Study Treatment Groups

- Group A (Active Stimulation Group): Patients receive standard ACS treatment plus active transcutaneous auricular vagus nerve stimulation (taVNS), twice daily for 20 minutes each session.
- Group B (Sham Stimulation Group): Patients receive standard ACS treatment plus sham taVNS treatment, twice daily for 20 minutes each session.

5.1 Randomization

5.1.1 Method for Generating Random Allocation Sequence

Stratified block randomization will be used: Eligible patients will be randomly assigned to Group A or B in a 1:1 ratio. Using R software, stratification will be based on age (two levels: 18-60 years, >60 years) and gender (two levels: male, female), resulting in 4 strata. Within each stratum, patients will undergo randomization with varying block sizes. The output will determine the stimulation device assigned to each patient.

5.1.2 Allocation Concealment

1. Personnel generating and safeguarding the random allocation sequence will not be involved in the trial. Research personnel will determine subject eligibility.
2. A central telephone randomization system will be used for allocation concealment. Once research personnel confirm a patient is eligible, they will notify the central randomization system (holder of the sequence) via telephone. The central system will record the subject's name and ID, then inform the researcher of the subject's group assignment.

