5.2 Blinding and Unblinding

This is a double-blind study. Patients, research personnel, and data analysts will be blinded.

6. Study Procedures

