6.1 Study Intervention Implementation Steps

1. For outpatients or inpatients who are 2 weeks to 12 months post-ACS PCI, a psychiatrist will conduct assessments using DSM-V, HAMD, and HAMA scales. Patients meeting criteria for mild to moderate depression will be advised to receive appropriate treatment. If they refuse and meet inclusion/exclusion criteria, they will sign informed consent, enroll in the clinical trial, and baseline data will be collected.

2. Device Usage Method

Eligible patients will receive transcutaneous auricular non-invasive vagus nerve stimulation while awake. The electrode and the patient's left ear target area will first be disinfected with 75% alcohol. An abrasive gel will then be applied to the left concha cymba and tragus area for gentle abrasion, wiped off, and the area disinfected again with alcohol. Conductive gel will be applied to the electrode output points. The electrode will be placed on the patient's left ear, ensuring the output points are positioned on the left tragus. Pulses will be delivered via the Xidian Keyue brand (Product No.: BS-TVNS600) vagus nerve stimulator. The stimulation current will be gradually increased to the maximum intensity tolerable by the patient, defined as the threshold intensity.

Active Stimulation Group: Stimulation at threshold intensity, with parameters: pulse frequency 20 Hz, pulse width 250 μ s, pulse current 0.5-3 mA. Stimulation cycle: 30 seconds ON, 30 seconds OFF.

Sham Stimulation Group: Device, parameter adjustment, and placement identical to the active group. The stimulator is programmed to deliver stimulation only for the first 5 seconds of each session, with no subsequent stimulation.

Both groups will undergo electrical stimulation twice daily for 20 minutes each session, for a total treatment duration of 8 weeks.

All patients will be trained on how to turn the stimulator on/off, attach the electrode to the ear and position it, and increase the intensity. All subsequent operations will be performed by the patient at home. Patients can obtain assistance via telephone

or site visits if they have questions. Each patient will be given a diary card to record usage date, duration, adverse reactions, and suggestions. Patients are required to complete daily entries, which will be checked during assessment visits.

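### The telephone randomization tells the calling researcher the patient's group, which contradicts the stated blinding of research personnel

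*Protocol*

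**What the plan says.** Four places in the protocol bear on who knows the allocation.

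- **Section 5.1.2, Allocation Concealment.** "Once research personnel confirm a patient is eligible, they will notify the central randomization system" by telephone. The system records the subject and will "then inform the researcher of the subject's group assignment". The only people kept apart are those who hold the sequence: "Personnel generating and safeguarding the random allocation sequence will not be involved in the trial".
- **Section 5, Study Treatment Groups.** The two labels are defined openly, as "Group A (Active Stimulation Group") and "Group B (Sham Stimulation Group").
- **Section 5.2, Blinding and Unblinding.** "Patients, research personnel, and data analysts will be blinded". No exception is given.
- **Section 5.1.1, on generating the sequence.** "The output will determine the stimulation device assigned to each patient".

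Section 6.1 adds that the sham device and its placement are the same as for active treatment, and that the difference lies in programming: "The stimulator is programmed to deliver stimulation only for the first 5 seconds of each session". It does not say who programs the devices, or when.

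**The concern.** Sections 5.1.2 and 5.2 cannot both hold for the researcher who makes the call. The letter gives no protection, because anyone with the protocol can translate A or B into active or sham. Carried out literally, section 5.1.2 unblinds one member of staff at each randomization, in a trial that is titled and described as double-blind.

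This matters because of the endpoint. The primary outcome (section 2.2.1) is the HAMD-17 score at Week 8, a rated scale that can move with the rater's expectations. Other steps also involve judgement: device training, telephone help and diary checks (section 6.1), lifestyle guidance (same section), withdrawal for poor adherence or poor lifestyle (section 6.3), and major protocol violations that are settled only at data review (section 9.2.2). If someone who knows the group takes part in any of these, the arms can come to differ for reasons other than stimulation.

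**Working it through.** The protocol gives no figure to reproduce here. The main check is to set the sections side by side.

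**Step 1. What is transmitted, and to whom.** Section 5.1.2 transmits the group, not a device number. The recipient is a researcher, in a step that research personnel start once they have confirmed eligibility.

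**Step 2. Whether the group label is masked.** It is not. Section 5 defines both letters.

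**Step 3. Whether this recipient is exempt from blinding.** No. Section 5.2 names research personnel as blinded and sets up no unblinded role.

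**Step 4. Whether the device wording cures it.** Sections 5.1.1 and 6.1 together are compatible with identical-looking devices, programmed in advance and handed out by code. However, no code, masked label or holder of a code list is described, and section 5.1.2 still has the group passed on. If coded devices are intended, that disclosure serves no purpose.

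**Step 5. Whether the informed person is kept away from outcomes.** The protocol does not say. Section 6.1 names a psychiatrist for the screening assessments. Section 6.2 lists the follow-up assessments without naming a rater. The training, support and diary tasks are written without naming who does them.

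**Step 6. Illustration of what a rater shift could do.** This is conditional on an unblinded rater, which the protocol neither states nor rules out.

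- Patients per arm: 60 planned, less 10% loss (section 9.1), gives 60 × 0.9 = 54.
- Assumed, not in the protocol: HAMD SD of 5 points; ratings shifted by 1 point between arms; no true effect.
- Standardized shift: 1 / 5 = 0.2.
- Noncentrality: 0.2 × √(54/2) = 0.2 × 5.196 = 1.04.
- Two-sided rejection rate at 0.05, normal approximation: 1 − Φ(1.96 − 1.04) + Φ(−1.96 − 1.04) ≈ 0.179 + 0.001 = 0.18.

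The same formula with other assumed values gives:

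| Assumed SD | Assumed shift | Noncentrality | Rejection rate |
|---|---|---|---|
| 5 | 0.5 | 0.52 | about 8% |
| 5 | 1 | 1.04 | about 18% |
| 7 | 0.5 | 0.37 | about 7% |
| 7 | 1 | 0.74 | about 12% |

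With no shift the rate is 5%.

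**The case against.** The best defence is that section 5.1.2 is loosely worded. On this view the trial means to mask by device: section 5.1.1 has the randomization output determine a device, section 6.1 makes the two devices identical apart from programming, and section 5.2 states the intention plainly. This is plausible as a guess at intent. It does not remove the conflict, because staff following section 5.1.2 would be told the group and nothing in the text replaces the group with a code.

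Other objections do stand and limit the point:

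- **The Week 8 HAMD.** A reader might infer that those ratings will be made unblinded. The protocol does not say so. It shows only that the caller is told the group, and it names no follow-up rater.
- **Other tasks.** A reader might also infer that the caller trains patients, answers device questions and checks diaries. The protocol assigns these tasks to no one, so this is possible but not stated.
- **The 18% figure.** It rests on an assumed SD and an assumed shift, and it describes a rater who knows the allocation. It is not an estimate of this trial's error rate.
- **Guessing later assignments.** Knowing past assignments could in principle help someone predict later ones. With varying block sizes within four strata (section 5.1.1) and a sequence holder outside the trial, this is minor. Central telephone allocation protects concealment before enrolment; the defect is in blinding after assignment.

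**Conclusion.** The protocol contradicts itself. Section 5.1.2, read with the definitions in section 5, tells the calling researcher the treatment of every patient. Section 5.2 says research personnel are blinded. The device wording in section 5.1.1 describes no masked code and does not settle the matter. This should be corrected before the procedure is used, since the trial is presented as double-blind and its primary endpoint is a rated scale.

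The disclosure applies to all 120 planned patients. Its effect on the result cannot be worked out from the document. Because no separation of roles is described, biased ratings or management are a risk and not an established fact. Under the assumed values in the illustration, the false-positive rate would lie between about 7% and 18%, and it would stay at 5% if the raters are in fact kept blind.

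**What to change.** Reconcile sections 5.1.1, 5.1.2 and 5.2 as follows:

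1. The central system gives the researcher only the code of the device to be dispensed. Codes must not fall into two recognizable series.
2. The sequence holder, who is outside the trial, keeps the list linking codes to groups.
3. Devices are programmed and labelled by someone who has no part in patient contact, outcome rating or analysis.
4. The code is broken only for a documented emergency unblinding of an individual patient, or after the blinded primary analysis is complete. Releasing the list at database lock would be too early, because section 5.2 also blinds the data analysts.
5. Section 6.2 states that whoever rates the HAMD has no access to the allocation.

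The cost is a few sentences in the protocol and coded labels on the devices. Someone outside the trial must do the programming and labelling; the protocol does not say who does this now. Sample size and analysis are unchanged.

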5.2 Blinding and Unblinding

This is a double-blind study. Patients, research personnel, and data analysts will be blinded.

6. Study Procedures

6.1 Study Intervention Implementation Steps

1. For outpatients or inpatients who are 2 weeks to 12 months post-ACS PCI, a psychiatrist will conduct assessments using DSM-V, HAMD, and HAMA scales. Patients meeting criteria for mild to moderate depression will be advised to receive appropriate treatment. If they refuse and meet inclusion/exclusion criteria, they will sign informed consent, enroll in the clinical trial, and baseline data will be collected.

2. Device Usage Method

Eligible patients will receive transcutaneous auricular non-invasive vagus nerve stimulation while awake. The electrode and the patient's left ear target area will first be disinfected with 75% alcohol. An abrasive gel will then be applied to the left concha cymba and tragus area for gentle abrasion, wiped off, and the area disinfected again with alcohol. Conductive gel will be applied to the electrode output points. The electrode will be placed on the patient's left ear, ensuring the output points are positioned on the left tragus. Pulses will be delivered via the Xidian Keyue brand (Product No.: BS-TVNS600) vagus nerve stimulator. The stimulation current will be gradually increased to the maximum intensity tolerable by the patient, defined as the threshold intensity.

Active Stimulation Group: Stimulation at threshold intensity, with parameters: pulse frequency 20 Hz, pulse width 250 μ s, pulse current 0.5-3 mA. Stimulation cycle: 30 seconds ON, 30 seconds OFF.

Sham Stimulation Group: Device, parameter adjustment, and placement identical to the active group. The stimulator is programmed to deliver stimulation only for the first 5 seconds of each session, with no subsequent stimulation.

Both groups will undergo electrical stimulation twice daily for 20 minutes each session, for a total treatment duration of 8 weeks.

All patients will be trained on how to turn the stimulator on/off, attach the electrode to the ear and position it, and increase the intensity. All subsequent operations will be performed by the patient at home. Patients can obtain assistance via telephone

or site visits if they have questions. Each patient will be given a diary card to record usage date, duration, adverse reactions, and suggestions. Patients are required to complete daily entries, which will be checked during assessment visits.

Both groups will receive guidance on medication and lifestyle intervention during follow-up (including CAD knowledge education, diet/exercise, sleep guidance, smoking cessation/alcohol limitation, and weight control).

6.2 Concomitant Treatment and Follow-up Visits

All enrolled patients will receive standard post-PCI medication and strict secondary prevention for coronary artery disease.

Follow-up visits will occur at 4, 8, 12, and 16 weeks post-randomization. Follow-up content includes: HAMA, HAMD, BDI, GAD-7, PCL-C, and SF-36 scale assessments; HRV measurement; echocardiography; venous blood tests; assessment of smoking/alcohol cessation and lifestyle improvement; record of follow-up visits (time, location, results); presence of angina or heart failure-related symptoms; occurrence of MACE (time, management, outcome); adverse reactions.

6.3 Patient Adherence and Withdrawal

Adherence: A trusting relationship will be established to ultimately improve subject adherence.

Withdrawal: Subjects found during follow-up to have poor treatment adherence, including self-discontinuation of device use, heavy smoking, and severely poor lifestyle/dietary habits; development of other serious new illnesses post-procedure that may affect study endpoints; loss to follow-up.

7. Evaluations

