2.2 Study Endpoints (or Evaluation Metrics)

2.2.1 Primary Endpoint (or Primary Evaluation Metric) and Definition

Hamilton Depression Rating Scale (HAMD) score at Week 8: The 17-item HAMD is convenient, has clear criteria, is easy to master, and can be used to assess depressive symptoms in various conditions including depression, bipolar disorder, and neurosis, being particularly suitable for major depressive disorder.

Scoring criteria:

No depressive symptoms: Total score ≤ 7 ; Mild depression: Total score ≥ 8 and ≤ 17 ; Moderate depression: Total score > 17 and ≤ 24 ; Severe depression: Total score > 24 .

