9.2 Analysis Populations

9.2.1 Full Analysis Set (FAS)

Based on the Intent-to-Treat (ITT) principle, includes all randomized subjects who received at least one treatment session from either the experimental or control group.

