9.2.2 Per Protocol Set (PPS)

Includes all subjects who completed the treatment regimen as specified in the protocol without major protocol violations. The exact definition of major protocol violations will be finalized during data review and may include (but is not limited to): failure to meet inclusion criteria, receipt of interfering treatments post-enrollment, poor adherence, visits outside specified time windows.

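### Section 6.3 withdraws patients for post-randomization events without saying whether outcome visits continue, so members of the ITT-based FAS may lose their Week 8 HAMD score

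*Protocol*

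**What the plan says.** Section 6.3, under its withdrawal label, lists "Subjects found during follow-up to have poor treatment adherence, including self-discontinuation of device use, heavy smoking, and severely poor lifestyle/dietary habits" and then "development of other serious new illnesses post-procedure that may affect study endpoints; loss to follow-up". The text is a list of reasons. It does not say what happens to a withdrawn patient's later visits or to data already collected.

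Section 4.3 gives a different list, confined to the patient's own choice: "Desire to pursue other treatments or voluntary withdrawal from the trial without specific reason".

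Section 9.2.1 defines the FAS: "Based on the Intent-to-Treat (ITT) principle, includes all randomized subjects who received at least one treatment session". Section 9.2.2 names, among possible major violations that exclude a patient from the PPS, "receipt of interfering treatments post-enrollment, poor adherence, visits outside specified time windows".

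The primary endpoint in section 2.2.1 is the "Hamilton Depression Rating Scale (HAMD) score at Week 8", compared between groups by a t-test or non-parametric test (9.3.1). Section 6.2 schedules assessments, including MACE, at Weeks 4, 8, 12 and 16 and does not mention patients already withdrawn.

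**The concern.** Every reason in 6.3 other than loss to follow-up describes something that happens after randomization to a patient who could still be rated. If such a patient is taken out of the study, the Week 8 score is not collected, and no later analysis choice can bring it back.

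The loss may also be related to outcome and to arm. The Introduction says that anxious and depressed patients often have unhealthy lifestyles and poor adherence, so by the protocol's own account these reasons go with the condition being measured. The illness clause is defined by its possible effect on the endpoints. Section 6.1 gives the active arm stimulation at the highest tolerable current in repeated cycles through each session, while sham delivers only the first 5 seconds, so reasons for stopping the device can differ between arms.

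What is at stake is whether the FAS comparison is the one 9.2.1 promises, or a comparison of the patients who stayed adherent and well. For MACE, a secondary endpoint, follow-up could be cut short in patients withdrawn for any of these reasons.

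**Working it through.** **1. Does withdrawal in 6.3 mean leaving the study?** The section does not say so outright. Three features point that way:
- A patient who has already stopped the device has no treatment left to be withdrawn from.
- Smoking and diet are not matters of device use.
- Loss to follow-up, which is by nature an exit from the study, is in the same list.

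Nothing elsewhere provides for visits after withdrawal.

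**2. The sections side by side.**

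| Event | 6.3 | 9.2.1 (FAS) | 9.2.2 (PPS) |
|---|---|---|---|
| Poor adherence, device stopped | Withdrawn | Stays a member after one session | Possible exclusion |
| Heavy smoking, poor lifestyle | Withdrawn | Stays a member | Not named |
| New serious illness | Withdrawn | Stays a member | Not named |

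FAS membership is untouched. What is at risk is the outcome of those members. The PPS exclusion for poor adherence has little work to do if such patients have already left.

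**3. Which withdrawals reach the primary endpoint?** Treatment lasts 8 weeks and visits fall at Weeks 4, 8, 12 and 16. Only withdrawal before the Week 8 rating can remove the primary score. A patient found non-adherent at the Week 8 visit is present and can be rated. Withdrawal at Week 12 or 16 affects only later secondary data.

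**4. Illustration of size.** The protocol gives no withdrawal rates by reason and no link between withdrawal and score, so the following are assumptions: no true effect, a standard normal outcome, 60 per arm (9.1), and 10% or 20% of each arm withdrawn before Week 8. Withdrawal is driven by a latent score with correlation ρ to a poor outcome. The test is a two-sided t-test at 0.05 on the patients who remain.

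If a share w is withdrawn, the mean of those who remain in that arm shifts towards better scores by

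bias = ρ × φ(z_w) / (1 − w)

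- w = 10%: φ(1.282) / 0.9 = 0.1755 / 0.9 = 0.195 SD at ρ = 1.
- w = 20%: φ(0.842) / 0.8 = 0.2800 / 0.8 = 0.350 SD at ρ = 1.

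Multiplying by ρ gives 0.039 and 0.070 SD at ρ = 0.2, and about 0.097 and 0.175 SD at ρ = 0.5. Simulation with exactly 6 or 12 of 60 removed (40,000 trials per case) gives slightly smaller values:

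| ρ | One arm only: bias, 10% to 20% withdrawn | One arm only: type I error | Both arms: bias | Both arms: type I error |
|---|---|---|---|---|
| 0.2 | 0.04 to 0.07 SD | about 6% | about 0 | about 5% |
| 0.5 | 0.09 to 0.17 SD | 8% to 14% | about 0 | about 6% |
| 1.0 | 0.19 to 0.34 SD | 20% to 46% | about 0 | 8% to 11% |

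In the one-arm case, withdrawal in the other arm is at the same rate but random. In the both-arms case the mean difference is unbiased, but removing the worst scores shrinks the observed SD, so the test is somewhat too liberal.

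**5. Unequal shares instead of unequal mechanisms.** If withdrawn patients score s SD worse than completers in both arms, the bias in the completers' difference is s × (w_A − w_B) in favour of the arm that loses more. With 15% against 5% and s = 0.5 to 1.0, this is 0.05 to 0.10 SD, with simulated type I error of about 6% to 9%. With 30% against 10% it is 0.10 to 0.20 SD and about 9% to 16%. With 10% in both arms it is zero and about 5%.

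**The case against.** The strongest reply is that the loss is inferred. Section 6.3 never says that visits stop or that data are discarded, the visit schedule in 6.2 exempts nobody, and listing poor adherence as a PPS exclusion suggests that such patients are still followed. This stands in part: the text is ambiguous, and the claim is about its natural reading. It does not remove the problem, because a protocol that intends continued assessment has to say so.

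A second reply is that missing-data handling belongs in an SAP, which is not shown. That is right for the analysis method, and for that reason the document does not support calling the FAS analysis a per-protocol analysis under another name. But an SAP cannot supply scores that were never taken.

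A reader might infer more than the text supports on three further points:
- **That MACE is undercounted.** The event that triggers a withdrawal would be recorded under 6.2, and the word "other" in "development of other serious new illnesses post-procedure that may affect study endpoints" can be read as excluding endpoint events. Only later events could be missed.
- **That 4.3 and 6.3 contradict each other.** One lists the patient's own choice, the other what is found at follow-up. Neither claims to be complete, so they can be complementary. They still need to be read as one rule.
- **That type I error reaches 46%.** That needs withdrawal wholly determined by outcome in one arm and random in the other, which nothing in the protocol establishes. Smoking, lifestyle and illness apply to both arms, and sham patients who feel no benefit can stop too.

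**Conclusion.** The point holds as a defect in the protocol's wording with a plausible effect on the primary comparison. Section 6.3 does not distinguish stopping the device from leaving the study and provides for no later assessment. Followed as it naturally reads, it costs FAS members their Week 8 HAMD when they are withdrawn before that rating, and it may cost MACE information after withdrawal.

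The reasons listed are plausibly informative, but neither the size nor the direction of bias follows from the document. Under the stated assumptions the effect runs from essentially none (weak correlation, or the same mechanism in both arms at low to moderate correlation) to 0.09–0.17 SD with 8–14% type I error for moderate, one-sided withdrawal. The 0.19–0.34 SD case is an extreme bound. The illustration shows only apparent benefit for the arm that loses its poor scorers. If that arm were sham, the sign would reverse.

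The point does not establish that the trial will be biased. It shows that the protocol leaves open an avoidable loss that cannot be repaired once it has happened.

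**What to change.** Reconcile 6.3 with 4.3, 9.2.1 and 9.2.2:
- Define discontinuation of the device and withdrawal from the study as separate events. When the device should be stopped is a clinical decision, on which no view is taken here.
- State that, unless consent is withdrawn, patients with poor adherence, device discontinuation, heavy smoking, poor lifestyle or a new illness continue the scheduled Week 4, 8, 12 and 16 outcome and MACE assessments.
- State that they are analysed in the FAS as randomized.
- Use poor adherence only to define the PPS.
- Record the date and reason for device discontinuation and for study withdrawal separately, by arm.

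The cost is a wording amendment, with Ethics Committee approval as section 11.1 requires, and the completion of some already scheduled visits for patients who would otherwise have been dropped.
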